3.3 Clinical Experience

CT1812 has been administered safely with good tolerability in over 60 healthy volunteers in a placebo-controlled Phase 1a trial (COG0101). Six single (10-1120 mg) and three multiple dose cohorts (QD, 14 days, 280-840 mg) were observed under close inpatient stay (N=6-8 treated, 2 placebo per cohort). Plasma concentrations of drug were shown to be approximately dose proportional across two orders of magnitude [0.13-14.93 mg (free base equivalent)/kg], and accumulation was minimal. Peak concentrations of CT1812 were reached within 1 to 2 hours and the plasma half-life was shown to be approximately 12 hours. Adverse events were mostly mild to moderate in severity and principally included headache, nausea, vomiting, diarrhea, constipation, abdominal pain, dyspepsia, upper respiratory tract infection, lightheadedness, syncope, myalgia, dizziness, rash and pain at the lumbar puncture site in those subjects who had lumbar punctures. There was only one AE of severe intensity, being an SAE of upper respiratory tract infection, occurring in one subject in the 840 mg dose of the MAD study, believed to be unrelated to study drug based on a similar pattern of URTIs in subjects receiving drugs other than CT1812 in the study unit during the same time period. One subject in the multiple dose cohort study developed a rash while on study drug. This subject showed improvement after discontinuing CT1812.

No evidence of renal toxicity was observed based on routine measures of renal function (serum creatinine, BUN) or cystatin C.

Four subjects in the MAD study showed an increase in liver function tests below 3X the upper limit of normal (including one subject on placebo). Subsequent studies will closely monitor liver enzyme parameters to determine if these were sporadic findings or possibly drug related.

A fed cohort (280 mg) single dose was compared to the fasting cohort of 280 mg and no significant food effect was observed. A multiple dose cohort of elderly (≥ 65 years old) healthy volunteers was dosed at 560 mg x 14 days, and their exposures were similar to the 840 mg younger healthy volunteer subjects.

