- a) Other primary degenerative dementia, (frontotemporal dementia, Huntington's disease, Creutzfeldt-Jakob Disease, Down syndrome, etc.).
 - b) Other neurodegenerative condition (amyotrophic lateral sclerosis, etc.).
 - c) Seizure disorder.
 - d) Other infectious, metabolic or systemic diseases affecting the central nervous system (syphilis, present hypothyroidism, present vitamin B12 or folate deficiency, other laboratory values etc.).
- 11) Clinically significant, advanced or unstable disease that may interfere with outcome evaluations, such as:
- a) Chronic liver disease, liver function test abnormalities or other signs of hepatic insufficiency (ALT, AST, alkaline phosphatase > 1.5 ULN, lactate dehydrogenase (LDH) > 1.5 x ULN).
 - b) Respiratory insufficiency which requires the use of supplemental oxygen.
 - c) Renal insufficiency eGFR < 50 mL/min based on the CKD-EPI formula.
 - d) Heart disease (myocardial infarction, unstable angina, heart failure, cardiomyopathy within six months before screening).
 - e) Bradycardia (<50 beats/min.) or tachycardia (>100beats/min.). If heart rate is below 50 beats/min or above 100 beats/min, the heart rate assessment may be repeated to assess eligibility.
 - f) Poorly managed hypertension (systolic >160 mm Hg and/or diastolic >95 mm Hg) or hypotension (systolic <90 mm Hg and/or diastolic <60 mm Hg).
 - g) Uncontrolled diabetes defined by HbA_{1c} >7.5% in subjects with diabetes, Only those subjects with known diabetes are required to get a HbA_{1c} at screen.
- 12) History of cancer within 3 years of screening with the exception of fully excised non-melanoma skin cancers or non-metastatic prostate cancer that has been stable for at least 6 months.
- 13) Seropositive for human immunodeficiency virus (HIV).
- 14) History of acute/chronic hepatitis B or C and/or carriers of hepatitis B (seropositive for hepatitis B surface antigen [HbsAg] or anti-hepatitis C [HCV] antibody).
- 15) Clinically significant abnormalities in screening laboratory tests, including:

- a) Hematocrit less than 35% for males and less than 32% for females, absolute neutrophil cell count of 1500/uL (with the exception of a documented history of a chronic benign neutropenia, absolute lymphocyte count <900/ uL), or platelet cell count of < 120,000/uL; INR >1.4 or other coagulopathy, confirmed by repeat assessment of:
 - i) Hematocrit
 - ii) Neutrophil count
 - iii) Lymphocyte count
 - iv) Platelet count

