12.1.4 Clinical Laboratory Tests

Hematology testing will include red blood cell count, erythrocyte mean corpuscular hemoglobin concentration (MCHC), erythrocyte mean corpuscular volume (MCV), hematocrit, hemoglobin, leukocyte count, and absolute counts of monocytes, neutrophils, basophils, eosinophils and platelets. Coagulation testing (prothrombin time [PT/INR]) will be performed at screening and Day 154 only.

Serum chemistry analyses will include glucose, calcium, albumin, total protein, sodium, potassium, bicarbonate, chloride, magnesium, blood urea nitrogen (BUN), creatinine, creatine kinase, alkaline phosphatase, ALT, AST, bilirubin, lipase, lactate dehydrogenase (LDH) and phosphorus.

In instances where either the AST or ALT are 2x the ULN these tests will be repeated and documented as an unscheduled visit.

Blood draws should occur within 1 hour of urine collection.

Urinalysis will include osmolality, creatinine, calcium, sodium, turbidity, color, specific gravity, pH, protein, glucose, ketones, bilirubin, blood, urobilinogen, nitrite, leukocytes, and microscopic particles. Urine should not be first morning void. Microscopic examination will be performed if urinalysis results are abnormal for bacteria, casts, epithelial cells, erythrocytes, or leukocytes. Urine should be collected within one hour of blood draws for hematology and chemistry panels. It should not be first morning void. Trace protein will be considered positive.

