## 6. GENERAL ANALYSIS CONSIDERATIONS

The statistical analyses will be reported using summary tables and listings. The International Council for Harmonisation of Technical Requirements for Pharmaceuticals for Human Use (ICH) numbering convention will be used for all tables, listings, and figures (TLFs). Unless otherwise noted, all statistical testing will be 2-sided and performed at the 0.05 significance level. Tests for the key efficacy endpoint of change from baseline in MoCA score at Month 6 will be declared statistically significant if the calculated  $P$  values following the sequential testing hierarchy described in Section 10.7 are  $<0.05$ . No adjustments for multiple comparisons will be made for the statistical testing of any other endpoints.

Continuous variables will be summarized by presenting the number of observations, means, standard deviations (SDs), medians, minimums, and maximums. Other summaries (e.g., quartiles, 95% confidence intervals [CIs]) may be used as appropriate.

Categorical variables will be summarized by presenting counts and percentages of subjects in corresponding categories. All possible categories as defined in the eCRF should be populated, even if they have zero counts. Percentages for missing values are omitted and do not account for the percent calculation of other categories. Percentages are based on the total category count excluding the missing category if not otherwise mentioned. In certain tables (e.g., AEs), the total number of subjects is used as the denominator. Footnotes will specify the percent basis in those cases.

All summary tables will be presented by treatment group. Baseline summaries will also include a total summary column.

Individual subject data obtained from the eCRFs, external vendors, central and local clinical laboratory and any derived data will be presented by subject in data listings.

The analyses described in this plan are considered a priori, in that they have been defined before breaking the blind.

Any analyses performed after breaking the blind will be considered post hoc and exploratory. Post hoc analyses will be labeled as such on the output and identified in the CSR.

All analyses and tabulations will be performed using SAS® statistical software, version 9.4 or higher (SAS Institute Inc). Tables, listings, and figures will be presented in RTF and PDF format.

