### 15.3 Clinical Laboratory Evaluation

Laboratory parameters (serum chemistry, hematology, coagulation, and continuous urinalysis parameters) will be summarized using descriptive statistics at baseline and at each post baseline time point. Changes from baseline will also be summarized.

In addition, shift tables relative to the laboratory normal range (i.e., low-normal-high at baseline versus low-normal-high at post baseline) will be provided to assess changes in serum chemistry and hematology laboratory values from baseline to each post baseline time point.

Subjects with elevated ALT, AST, ALT or AST  $\geq 3 \times$  ULN, ALT, AST, ALT or AST  $\geq 5 \times$  ULN, ALT, AST, ALT or AST  $\geq 10 \times$  ULN, and ALT, AST, ALT or AST  $\geq 20 \times$  ULN will be summarized. Categories will be cumulative, i.e. a subject with an elevation of AST  $\geq 5 \times$  ULN will also appear in the categories  $\geq 3 \times$  ULN.

Separate listings for chemistry, hematology, coagulation, liver function, and urinalysis results will be presented.

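### SAP 15.3 has no ALT/AST category between ULN and 3 x ULN, so no specified table counts subjects per arm who ever exceeded ULN or reached the protocol's 2 x ULN retest level

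*SAP*

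**What the plan says.** SAP 15.3 plans four things for the transaminases.

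- **Threshold counts.** The paragraph that opens "Subjects with elevated ALT, AST, ALT or AST" counts subjects at or above 3, 5, 10 and 20 x ULN, for ALT, AST and either. The counts nest upward: "Categories will be cumulative, i.e. a subject with an elevation of AST" of 5 x ULN or more is also counted at 3 x ULN. A subject whose peak stays below 3 x ULN is in no row.
- **Shift tables.** For serum chemistry and hematology, "shift tables relative to the laboratory normal range (i.e., low-normal-high at baseline versus low-normal-high at post baseline) will be provided", at each post-baseline time point. Protocol 12.1.4 places ALT and AST in serum chemistry.
- **By-visit summaries.** Laboratory parameters "will be summarized using descriptive statistics at baseline and at each post baseline time point", with changes from baseline.
- **A liver function listing.**

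SAP 6 adds: "All summary tables will be presented by treatment group".

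The protocol has three relevant passages. Section 12.1.4 sets a retest level: "In instances where either the AST or ALT are 2x the ULN these tests will be repeated and documented as an unscheduled visit". Section 3.3 reports four subjects in the multiple-dose study, one of them on placebo, with liver test rises below 3 x ULN, and continues: "Subsequent studies will closely monitor liver enzyme parameters to determine if these were sporadic findings or possibly drug related". Section 8.3 excludes subjects with "ALT, AST, alkaline phosphatase > 1.5 ULN", so that criterion alone permits entry with values above ULN.

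**The concern.** Safety and tolerability is the primary objective, and liver test elevations recur in Protocol 3.3: the rises below 3 x ULN above, one ALT of 4.7 x ULN at 560 mg, two withdrawals for mild increases judged probably related, and several episodes of unstated size in the ongoing Alzheimer's study. The question that Protocol 3.3 leaves open concerns rises below 3 x ULN, and the SAP's threshold table starts where that range ends.

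Two simple by-arm counts are missing: how many subjects were ever above ULN after baseline, and how many reached 2 x ULN. The shift tables do not supply them. They work visit by visit, so a transient rise at different visits in different subjects never adds up to one incidence. They also put every value above ULN into a single category. The trial could then finish without a direct subject-level answer to a question that the protocol itself raises.

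**Working it through.** **1. Where a given peak is summarized under the SAP as written**

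| Highest post-baseline ALT or AST | Threshold table | Shift table at that visit | Other by-arm summaries |
|---|---|---|---|
| 1.05 x ULN | no row | high | by-visit statistics; AE if clinically significant |
| 2.0 to 2.9 x ULN | no row | high | the same, plus a protocol retest |
| 3 x ULN or more | counted | high | the same |

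The first two rows differ in what the protocol requires of the site, but not in any categorical laboratory table.

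**2. Retests.** The repeat at 2 x ULN is recorded as an unscheduled visit. SAP 10.4 summarizes data by nominal visit, and SAP 10.2 mentions unscheduled visits only for deriving baseline. No rule says whether a post-baseline retest enters a laboratory table.

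**3. The plan's own figure.** The documents give no rate, power or expected count for liver findings, so there is nothing to reproduce. The two illustrations below show scale only.

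**4. Illustration from the counts in Protocol 3.3.** Inputs: four subjects with rises below 3 x ULN, one on placebo; three multiple-dose cohorts, each with 6 to 8 treated and 2 placebo. That gives 3 of 18 to 24 on active drug and 1 of 6 on placebo.

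- Active: 3/24 = 12.5% (exact 95% CI 2.7% to 32%) to 3/18 = 16.7% (3.6% to 41%). Scaled to 80 active subjects: 80 x 3/24 = 10 to 80 x 3/18 = 13.3.
- Placebo: 1/6 = 16.7% (0.4% to 64%). Scaled to 40: 40 x 1/6 = 6.7.

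These counts show no excess on drug, and they come from 14 days at 280 to 840 mg in healthy volunteers. They show only that, if similar rates held here, about 10 to 13 active and 7 placebo subjects could have rises that the threshold table does not count.

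**5. Illustration from an assumed distribution.** Assumptions, none from the documents: the peak ALT/ULN ratio is lognormal, with placebo median 0.7 and log-SD *s* of 0.45 to 0.55, and drug multiplies the peak by *m* = 1.5. The expected number per 40 at or above threshold *t* is

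40 x [1 − Φ((ln *t* − ln(0.7 *m*)) / *s*)].

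Example: *t* = 2, *m* = 1.5, *s* = 0.45 gives (ln 2 − ln 1.05)/0.45 = 1.432, an upper tail of 0.076, and 40 x 0.076 = 3.0.

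| Threshold | Placebo, per 40 | Drug, per 40 |
|---|---|---|
| above ULN | 8.6 to 10.3 | 21.4 to 21.7 |
| 2 x ULN or more | 0.4 to 1.1 | 3.0 to 4.8 |
| 3 x ULN or more | 0.0 to 0.2 | 0.4 to 1.1 |

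Under these assumptions the 2 x ULN row holds about four to eight times as many drug-arm subjects as the lowest row planned. With *m* between 1.3 and 1.8 the ratio runs from about 3.5 to 10.

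**The case against.** Much can be said for the plan as written, and most of it stands.

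- **Rises below 3 x ULN are shown by arm.** A reader might infer that they are never graded by treatment group, or that most of the graded information is thrown away. The documents do not support either. Shift tables are by arm, change from baseline keeps the full scale, every value is listed, and Protocol 12.2.1 makes a clinically significant laboratory abnormality an adverse event. That route can catch small rises, as the mild liver test TEAEs in Protocol 3.3 show. What is absent is grading by multiples of ULN: AE severity is a functional scale.
- **2 x ULN is a retest trigger, not a dosing action.** Dosing rules in Protocol 6.3.1 begin above 3 x ULN, and the SAP's first two rows follow them, apart from > versus ≥.
- **A high-to-high shift is probably uncommon.** The 1.5 x ULN criterion would let a subject start above ULN, so that doubling shows no shift. But Protocol 9.2.1 excludes subjects whose abnormal screening result persists on repeat. A Day 1 rise remains possible.
- **The liver signal is not confined to rises below 3 x ULN**, and Protocol 3.3 promises monitoring across later studies, not a particular table.
- **The 10 and 20 x ULN rows** might be expected to stay empty. The documents do not establish that, and a zero there is informative.
- **Appendix C** of the SAP is not reproduced in the available text, so finer rows in the table shells cannot be excluded.

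The sharpest objection uses the illustration itself. Under the same assumptions, the number above ULN separates the arms better than the 2 x ULN row: rounded counts of 9 vs 22 or 10 vs 21 give Fisher p of about 0.005 to 0.02, against 0.20 to 0.24 for 0 vs 3 or 1 vs 5. The 2 x ULN row alone would thus be a weak addition. But those stronger counts are of each subject's peak, whereas the planned high category is per visit. The objection therefore supports adding a peak-based row above ULN as well.

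**Conclusion.** The point holds as a minor, cheap improvement, not an error. SAP 15.3 specifies no ALT/AST category between ULN and 3 x ULN, and no table of how many subjects per arm ever exceeded ULN or reached 2 x ULN. That conclusion comes from the text and needs no modelling. It is subject only to the unseen table list. No estimate, test, sample size or dosing rule is affected.

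The size of the gain is uncertain. The lognormal figures depend wholly on assumed inputs, and the counts in Protocol 3.3 are too few, and from too different a setting, to predict this trial.

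**What to change.** In the existing cumulative table of SAP 15.3, add two rows each for ALT, AST and ALT-or-AST: above ULN, and at least 2 x ULN. Base them on each subject's worst post-baseline value, present them for each dose and for the combined CT1812 group against placebo, and state that unscheduled retests are included. Also say whether early termination visits before Day 170 count, since SAP 10.4 otherwise leaves those data to the listings.

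The cost is a few table rows and one sentence of derivation, with no new data. The low-threshold rows will carry more background noise, which the placebo column makes visible.

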## 15.4 Vital Signs

Vital signs and other measures (systolic and diastolic blood pressure, temperature, respiration rate, pulse rate, weight) will be summarized using descriptive statistics at baseline and at each postbaseline time point. Changes from baseline will also be summarized.

Separate listings for vital signs results will be presented.

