3.2.3 Nonclinical Safety Studies

Two hERG (human Ether-à-go-go Related Gene) assays were performed to assess effects of CT1812 on the rapidly activating delayed rectifier potassium channels (IKr) using channels stably transfected and over-expressed in Chinese Hamster Ovary cells. Using whole-cell patch clamp electrophysiology, CT1812 was tested in both studies in duplicate at concentrations of 1, 3, 10, and 30 mM. Mean IC_{50} values of 26 mM and 0.6 mM were determined in the first and second assay, respectively. Reasons for the differing results are unknown. However, no ECG effects were noted in the telemeterized dog cardiovascular safety study or in the multiple-dose dog pivotal toxicology study when tested up to high-dose mean C_{max} values of approximately 4 μM .

Safety pharmacology studies with rats revealed no apparent effects on CNS or pulmonary parameters following single oral dosages that exceeded the maximum tolerated dose in this species.

General toxicology studies with rats and dogs following oral dosing of CT1812 revealed dose-limiting toxicity that manifested as degenerative changes in the proximal tubules of kidney, hypercalcemia, and vascular mineralization and/or degeneration involving multiple tissues and organs in each species. Tolerable and intolerable dosages and exposures, characterized with each species, informed the selection of dosages for this trial.

Additionally, toxicology studies revealed several test article-related clinical laboratory changes, including elevated serum creatinine and/or BUN that correlated with mild weight loss, elevated serum calcium and reduced urinary specific gravity. The exact mechanism for these changes cannot be determined from those studies. Serum and urine tests will be performed in this trial to evaluate the effect of study drug administration on renal function (including serum creatinine, serum calcium, urine calcium).

Genetic toxicology studies revealed no positive responses in bacterial and mammalian in vitro assays, or in an in vivo mouse bone marrow micronucleus assay when tested up to maximally feasible dosages.

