## 15.6 Electrocardiogram

ECG parameters (ventricular rate, RR, PR, QRS, QT, QTcF and QTcB) will be summarized using descriptive statistics at baseline and at each post baseline time point. Changes from baseline will also be summarized. Interpretation results will present the number and percentage of normal, abnormal not clinically significant, and abnormal clinically significant results at each visit.

In addition, a categorical summary of abnormal corrected QT interval values will be presented. At each time point, the number of subjects with QTcF values of >450 ms, >480 ms, and >500 ms will be presented. At each postbaseline time point, the number of subjects with change from baseline values in QTcF of >30 ms and >60 ms will be presented.

Electrocardiogram results will be presented in a listing.

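### Vital signs and weight get only by-visit continuous summaries and listings; no table counts, by arm, the subjects with a marked value or change

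*SAP*

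**What the plan says.** SAP 15.4 covers systolic and diastolic blood pressure, temperature, respiration rate, "pulse rate, weight) will be summarized using descriptive statistics at baseline and at each postbaseline time point". It adds "Changes from baseline will also be summarized" and "Separate listings for vital signs results will be presented". It plans nothing else.

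SAP section 6 defines the continuous summary: "Continuous variables will be summarized by presenting the number of observations, means, standard deviations (SDs), medians, minimums, and maximums", with quartiles and confidence intervals optional. Protocol 14.1 gives the same set, and protocol 14.4.2 plans absolute values and change from baseline for vital signs.

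The neighbouring sections go further. SAP 15.3 adds shift tables for chemistry and hematology and cumulative ALT/AST categories at 3, 5, 10 and 20 times ULN. SAP 15.6 says that "a categorical summary of abnormal corrected QT interval values will be presented" and counts subjects with QTcF above 450, 480 and 500 ms and with increases above 30 and 60 ms.

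Protocol 8.3 already holds numerical limits, as eligibility criteria only. Criterion 11e covers pulse below 50 or above 100 beats/min. Criterion 11f reads "Poorly managed hypertension (systolic >160 mm Hg and/or diastolic >95 mm Hg) or hypotension (systolic <90 mm Hg and/or diastolic <60 mm Hg".

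SAP 10.4 places data in summary tables by nominal visit. The Day 182 label serves both end of study and early termination, and early-termination data from before study Day 170 are listed but not tabulated.

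**The concern.** Safety and tolerability are the primary objective, and protocol 5.2.1 names change in vital signs as a safety endpoint. Marked hypotension, bradycardia or weight loss, if it occurs, is likely to affect a minority of subjects. The natural summary is then how many subjects per arm had it, and the SAP has no such table for vital signs.

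The program's background gives some reason to look. Phase 1 adverse events included "lightheadedness, syncope, myalgia, dizziness" (protocol 3.3), and the animal studies found "elevated serum creatinine and/or BUN that correlated with mild weight loss" (protocol 3.2.3). Subjects who stop early are a group in whom such changes would be of interest, and their last visit may be missing from the tables.

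**Working it through.** **1. Which safety sections count subjects?** Neither document states a figure for vital signs, so the main check is to set the SAP sections side by side.

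| SAP section | Count or category by arm? |
|---|---|
| 15.1 Adverse events | Yes: subject incidence |
| 15.2 Exposure | Yes: dose interruption, compliance bands |
| 15.3 Laboratory | Yes: shift tables, ALT/AST multiples |
| 15.4 Vital signs and weight | **No** |
| 15.5 Physical examination | Yes: three-level result |
| 15.6 ECG | Yes: QTcF thresholds, three-level interpretation |
| 15.7 C-SSRS | Yes: any post-baseline positive answer |

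**2. What the planned statistics would show.** The following is an illustration. The 40 per arm is from SAP section 5. The size of fall, the share affected, the SDs and the 75 kg weight are assumptions.

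Suppose 4 of 40 subjects in one arm (10%) have a 30 mm Hg systolic fall.

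- Mean shift = 0.10 × 30 = 3.0 mm Hg.
- The affected minority adds variance 0.1 × 0.9 × 30² = 81 to that arm, so the SE of the between-arm difference is √[(SD² + 81)/40 + SD²/40].

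| Assumed SD of change (mm Hg) | SE of difference | Shift ÷ SE | SD in affected arm, √(SD² + 81) |
|---|---|---|---|
| 10 | 2.65 | 1.13 | 13.5 |
| 12 | 3.04 | 0.99 | 15.0 |
| 15 | 3.64 | 0.82 | 17.5 |
| 20 | 4.69 | 0.64 | 21.9 |

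For weight, 10% of subjects losing 7% of 75 kg gives a mean shift of 0.10 × 0.07 × 75 = 0.53 kg. The SE, SD × √(2/40), is 0.45 to 0.89 kg for an SD of 2 to 4 kg.

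The mean is therefore a weak indicator. The SD would widen somewhat.

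**3. What the minimum adds.** The minimum change does show the worst fall in each arm at each visit. It describes one subject, so it cannot separate one affected subject from four, or show whether the extremes at different visits come from the same person. It also has a large background value. For 40 normally distributed changes with no drug effect, the expected minimum is about 2.16 SDs below the mean (simulation), which is 26 mm Hg for an SD of 12 and 32 mm Hg for an SD of 15. Placebo could show a minimum much like that of an affected arm.

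**4. Early termination.** SAP 10.4 stands in the efficacy section but is worded for summary tables in general. If it governs safety tables too, a subject with a marked value at an early-termination visit before Day 170 is absent from the mean, SD, minimum and maximum for that visit. If it governs efficacy only, this part of the point falls away.

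**The case against.** The strongest reply is that outliers are not hidden. The plan requires SD, median, minimum and maximum for values and changes, and lists every result. A reader might infer that vital signs are reported only as means, with marked changes averaged away. The documents do not support that, because a 30 mm Hg fall at a tabulated visit could be no smaller than the reported minimum change and would appear in the listing.

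Counts by arm also exist in part elsewhere. An unfavorable sign can be an adverse event (protocol 12.2.1) and is then counted under SAP 15.1. ECG interpretation and physical examination findings are categorized, and the medical monitor and DSMB review safety data during the trial. This stands, but adverse event reporting depends on investigator judgment, and the SAP did not treat it as enough for laboratory values or QTcF.

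A reader might also infer that a count table would give a decisive contrast, such as 4/40 against 0/40. It need not. A fall of 30 mm Hg crosses the systolic limit of 90 only from a starting value below 120, background crossings will occur on placebo, and even 4/40 against 0/40 has a two-sided Fisher p of about 0.12. Nor does the SAP plan tests on vital signs. The case for the table is description, not power.

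The background signal is modest. The Phase 1 events are not split by arm and came from single doses up to 1120 mg and multiple doses of 280 to 840 mg. The animal weight loss was mild. Finally, SAP 15.4 follows protocol 14.4.2, so there is no contradiction between the documents.

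**Conclusion.** The point holds as a gap in presentation of low severity. The planned tables show the distribution of vital signs and weight at each nominal visit, including its extremes, but not how many subjects per arm had a marked value or change. Vital signs are the one domain in SAP 15.1 to 15.7 treated this way, and no reason is given.

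The absence of a count rests on the text alone. The illustration of how little the mean moves rests on the assumed SDs, share affected and size of fall. The early-termination part depends on SAP 10.4 applying to safety tables, which the SAP leaves open. Nothing here shows that a vital-sign effect exists, or that individual outliers would go unreported.

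**What to change.** Before unblinding, add one table to SAP 15.4 giving the number and percentage of subjects, by arm and for CT1812 combined, with:

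- any post-baseline pulse or blood pressure value outside the limits in exclusions 11e and 11f, among subjects inside the limit concerned at baseline;
- change from baseline in blood pressure in prespecified categories, needed because a large fall may not cross a fixed limit;
- percent weight loss from baseline in prespecified categories.

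Count each subject once on the worst post-baseline value, including unscheduled and early-termination visits whatever their study day. State in SAP 10.4 whether the Day 170 rule applies to safety tables. The sponsor should choose the change and weight cut-offs; 5% and 7% weight loss are examples not taken from the documents. All of these are reporting thresholds and change no clinical rule.

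The cost is one table from data already collected. The downside is that background crossings, including trivial ones near a limit, will appear in every arm, with the placebo column as the reference. Timing matters because SAP section 6 classes any analysis performed after the blind is broken as post hoc; a table added later should be labeled so.
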